**Appendix D. Pooled Cohort Equations From 2013 ACC/AHA Cardiovascular Risk Assessment Guideline**

Online ASCVD Risk Estimator: <https://www.acc.org/tools-and-practice-support/mobile-resources/features/2013-prevention-guidelines-ascvd-risk-estimator>.

Parameter (Patient Level)	Cohorts			
	Men		Women	
	Non-African American/Black	African American/Black	Non-African American/Black	African American/Black
Corresponding Coefficient ( $\beta_i$ )				
$x_1 = \ln \text{Age (years)}$	$\beta_1 = 12.344$	$\beta_1 = 4.01$	$\beta_1 = -29.799$	$\beta_1 = 17.114$
$x_2 = (\ln \text{Age})^2$	$\beta_2 = \text{N/A}^*$	$\beta_2 = \text{N/A}$	$\beta_2 = 4.884$	$\beta_2 = \text{N/A}$
$x_3 = \ln \text{Total Cholesterol (mg/dL)}$	$\beta_3 = 11.853$	$\beta_3 = 5.36$	$\beta_3 = 13.540$	$\beta_3 = 0.940$
$x_4 = \ln \text{Age} * \ln \text{Total Cholesterol}$	$\beta_4 = -2.664$	$\beta_4 = \text{N/A}$	$\beta_4 = -3.114$	$\beta_4 = \text{N/A}$
$x_5 = \ln \text{HDL-C (mg/dL)}$	$\beta_5 = -7.990$	$\beta_5 = -0.307$	$\beta_5 = -13.578$	$\beta_5 = -18.920$
$x_6 = \ln \text{Age} * \ln \text{HDL-C}$	$\beta_6 = 1.769$	$\beta_6 = \text{N/A}$	$\beta_6 = 3.149$	$\beta_6 = 4.475$
$x_7 = \ln \text{Treated Systolic BP (mm Hg)}$	$\beta_7 = 1.797$	$\beta_7 = 1.916$	$\beta_7 = 2.019$	$\beta_7 = 29.291$
$x_8 = \ln \text{Age} * \ln \text{treated Systolic BP}$	$\beta_8 = \text{N/A}$	$\beta_8 = \text{N/A}$	$\beta_8 = \text{N/A}$	$\beta_8 = -6.432$
$x_9 = \ln \text{Untreated Systolic BP (mm Hg)}$	$\beta_9 = 1.764$	$\beta_9 = 1.809$	$\beta_9 = 1.957$	$\beta_9 = 27.820$
$x_{10} = \ln \text{Age} * \ln \text{Untreated Systolic BP}$	$\beta_{10} = \text{N/A}$	$\beta_{10} = \text{N/A}$	$\beta_{10} = \text{N/A}$	$\beta_{10} = -6.087$
$x_{11} = \text{Current Smoker (1=yes 0=No)}$	$\beta_{11} = 7.837$	$\beta_{11} = 0.549$	$\beta_{11} = 7.574$	$\beta_{11} = 0.691$
$x_{12} = \ln \text{Age} * \text{Current Smoker}$	$\beta_{12} = -1.795$	$\beta_{12} = \text{N/A}$	$\beta_{12} = -1.665$	$\beta_{12} = \text{N/A}$
$x_{13} = \text{Diabetes (1=Yes 0=No)}$	$\beta_{13} = 0.658$	$\beta_{13} = 0.645$	$\beta_{13} = 0.661$	$\beta_{13} = 0.874$
Parameter (Cohort Level)	Given Value (For each cohort)			
a=Cohort Constant	61.18	19.54	-29.18	86.16
b=Baseline Survival	0.9144	0.8954	0.9665	0.9533

For Patient level parameters ( $x_i$  for  $i$  in 1:13), multiply that patient's value by the appropriate coefficient ( $\beta_i$ ) to get the patient-parameter value ( $z_i$ ) then sum up the patient-parameter value of all the relevant parameters ( $z_1, z_2, \dots, z_{13}$ ) to get the patient sum ( $y$ ). Then, the estimated 10-year risk of first hard ASCVD is calculated as 1 minus the baseline survival, raised to the power of the exponent of the patient sum minus the Mean Value. Written as an equation this can be expressed as:

$$y = \sum_{i=1}^n \beta_i x_i$$

$$\text{Estimated 10 - year risk of a first hard ASCVD} = 1 - b^{e^{y-a}}$$

\*N/A means that particular parameter is not included in the calculation for that subgroup (can be thought of as  $\beta_i$  being equal to 0.)

Note:  $a$ =Cohort Constant,  $b$ =Baseline Survival, and  $\beta_i$  =Cohort Specific Parameter  
Coefficient are cohort specific values (eg, African American Woman), and  $x_i$  are patient specific values.

Example: White 43-year-old woman with Total-cholesterol=211mg/dL, HDL-C=52mg/dL, untreated systolic BP=117 mm Hg, smoker without diabetes. For this patient  $\beta_8$  and  $\beta_{10}$  are not used due to being in the white female cohort.  $\beta_7$  is also unused as they have untreated Systolic BP.  $x_{11}=1$  and

$x_{12}=\ln(\text{age})*1$  as they are a smoker and  $x_{13}, x_{14}=0$  as they do not have diabetes. In this case  $a=-29.18$ ,  $b=0.9665$  and  $\beta_i$  will be selected from the same column as  $a$  and  $b$ . The Final value this gives is

$$1 - 0.9665^{\exp(-27.546-(-29.18))} = 0.026 \text{ or } 2.6\% \text{ risk of hard ASCVD in 10-years}$$

---

**Appendix E. Details of PK or PK/PD Methods for Modeling**

Not applicable for this study.

## Appendix F. Analytical Windows

### Analytical Study Week Assignments

Analytical windows will be used to assign parameter measurements to study weeks. The algorithm is provided below.

Selected endpoints will be summarized by scheduled study visits in descriptive analyses. Since the actual visits may not exactly coincide with their scheduled visit day, the actual visit day is mapped to the study visit generally by non-overlapping consecutive intervals covering the entire time continuum. The mapping intervals for all distinct schedules are summarized in the following table:

**Table 12-1. Analytical Window for Primary Analysis**

Analytical Study Week	Week 8	Week 10	Week 12
Scheduled Visit Day	57	71	85
Body Weight, Waist circumference, HbA1c, HCV, Hepatitis C viral load, hsCRP, Anti-evolocumab antibodies			>1
Chemistry, Hematology, Urinalysis	(1, 71]		(71, 91]
Vital Signs, Fasting Lipids, ApoA1, ApoB, Lp(a), PCSK9,	(1, 63]	(63, 77]	(77, 91]

**Table 12-2. Analytical Window for Subjects Meeting PD 953 Used in Sensitivity Analysis**

Analytical Study Week	Week 8	Week 10	Week 12
Scheduled Visit Day	57	71	85
Body Weight, Waist circumference, HbA1c, HCV, Hepatitis C viral load, hsCRP, Anti-evolocumab antibodies			>1
Chemistry, Hematology, Urinalysis	(1, 71]		(71, 115]
Vital Signs, Fasting Lipids, ApoA1, ApoB, Lp(a), PCSK9,	(1, 63]	(63, 84]	(84, 99]

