7. STUDY PROCEDURES

Screening assessments and study procedures outlined in this section and in [Table 2](#) can only be performed after obtaining a signed informed consent. This includes any discontinuation of the subject's medication for the purpose of participation in this study.

It is very important to attempt to perform study procedures and obtain samples at the precise timepoints stipulated in [Table 2](#). When it is not possible to perform the study visit at the exact timepoint, the visit may be performed within the acceptable visit window

as defined in [Table 2](#). If a study visit is missed or late, including visits outside the visit window, subsequent visits should resume on the original visit schedule.

Any assessments at prior visits should not be duplicated at subsequent visits, with the exception of screening and rescreening visits, if possible, all study procedures for a visit should be completed on the same day. Subsequent study visits should resume on the original schedule. Missed assessments at prior visits should not be duplicated at subsequent visits.

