7.2 General Study Procedures

7.2.1 Study Visit Definitions and Windows

After signing the ICF, potential subjects will be evaluated to determine whether they fulfill the entry requirements listed in [Section 4.1](#). At screening, the subject should be reminded that participation in the study is contingent upon his or her screening test results. The screening period begins the day the subject signs the ICF, and ends (after 28 days) when the subject is randomized to receive the first dose of investigational product or fails the enrollment criteria.

Refer to the applicable supplemental central laboratory, IVRS/IWRS, and study manuals for detailed collection and handling procedures.

Subjects should be randomized before or on the day 1 visit, and initiate their first dose of investigational product within 5 days of randomization.

The following visit windows (\pm 3 days) will apply to all visits during the treatment period of the study:

- Week 8
- Week 10
- Week 12
- Week 14 (Q2W subjects only)

Study procedures for a specific visit may be completed on multiple days as long as all the procedures are completed within the visit window.

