## 9.5 Efficacy Analyses

**Table 9-1. Primary Efficacy Endpoint Summary Table**

Endpoint	Primary Summary and Analysis Method (Specify Analysis Set if FAS is Not Used)	Sensitivity and/or Supplementary Analysis

Mean percent change from baseline at weeks 10 and 12 in LDL-C

Percent change from baseline at week 12 in LDL-C

	Repeated Measures Model assuming Missing at Random (MAR), including all values observed (on and off IP)	
Sensitivity analysis:
 

Multiple imputation to handle missing primary variables

Applying a separated analytical window to subjects who have protocol deviation code 953 (COVID-19 out-of-window visit).

 
Supplementary analysis:
 

Primary analysis will be repeated using CAS

Non-parametric analyses will be performed if assumption of normality is violated

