### 9.5.1 Analyses of Primary Efficacy Endpoint(s)

To assess the co-primary endpoints as described in the co-primary estimands a repeated measures linear effects model including all observed values (on and off treatment) will be used on the FAS in each dose frequency to compare the efficacy of evolocumab with placebo. The repeated measures model will include terms for treatment group, stratification factor, scheduled visit and the interaction of treatment with scheduled visit. Missing values will not be imputed for primary analysis.

To account for the repeated LDL-C measurements within a subject across the visits, the repeated measures linear effects model will use an unstructured covariance.

Multiplicity adjustment procedures are defined in [Section 9.1](#).

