#### 9.5.1.1 Sensitivity Analyses of Co-primary Endpoints

To evaluate the robustness of the analysis results, sensitivity analyses will be performed as follows:

- Multiple imputation assuming MAR to handle missing primary variables
  - It will be assumed that the missing percent change values will be normally distributed with a mean 0 and a variance-covariance matrix the same as the observed variance-covariance matrix from subjects in the placebo group and have missing endpoint data.
  - If there are at least 25 subjects **in each treatment group** who discontinue IP but have non-missing endpoint data, an additional multiple imputation will be carried out utilizing the information from these subjects to impute the missing data for subjects **who discontinue IP** and have missing endpoint data.
- **An additional sensitivity analysis will be performed to evaluate the impact of COVID-related out of window visits. Primary analysis will be repeated using FAS. The subjects meeting protocol deviation code 953 (out-of-window visit) will use the analysis window defined in [Table 12-2](#) and the remaining subjects will use the analysis window defined in [Table 12-1](#) (ie, same visit window as the primary analysis).**

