### **Handling multiple records assigned to an analytical study week:**

If there is more than one record in a study week interval, the analytical record for that specific study week will be defined as the record closest to the scheduled visit day of that specific study week ( $7 \times$  study week + 1). If two records are equidistant from the scheduled day, then the earlier record will be chosen. If there are multiple records on the same day, the last record will be used.

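### The COVID-19 out-of-window sensitivity analysis starts Week 12 at Day 85 for every code-953 subject, so on-time Week 12 lipid samples from Days 82-84 are lost or counted as Week 10

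*SAP*

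**What the plan says.** SAP 9.5.1.1 adds a repeat of the primary analysis on the FAS to judge the effect of COVID-related out-of-window visits. The rule is set by subject: "The subjects meeting protocol deviation code 953 (out-of-window visit) will use the analysis window defined in" Table 12-2, and everyone else stays on Table 12-1. Table 9-1 describes the analysis in the same way.

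The lipid rows of the two tables in Appendix F, the second of which is titled "Analytical Window for Subjects Meeting PD 953 Used in Sensitivity Analysis", are:

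| Table | Week 8 | Week 10 | Week 12 |
|---|---|---|---|
| 12-1 (primary) | (1, 63] | (63, 77] | (77, 91] |
| 12-2 (code 953) | (1, 63] | (63, 84] | (84, 99] |

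Appendix F assigns records by study day, in general through "non-overlapping consecutive intervals covering the entire time continuum". If an interval holds several records, "the analytical record for that specific study week will be defined as the record closest to the scheduled visit day". For the model being repeated, SAP 9.5.1 states: "Missing values will not be imputed for primary analysis".

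On visit timing, Protocol 7.2.1 sets a window of ± 3 days that "will apply to all visits during the treatment period of the study". Protocol Section 7 adds: "If a study visit is missed or late, including visits outside the visit window, subsequent visits should resume on the original visit schedule".

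**The concern.** Table 12-2 is meant to recover samples taken late. To make room for late Week 10 samples it moves the boundary between Weeks 10 and 12 from Day 77 to Day 84, which is inside the permitted Week 12 window. Because the table follows the subject and not the coded visit, someone coded for a late Week 8 or Week 10 visit who then returns to schedule, as the protocol directs, can have a valid Week 12 sample taken out of Week 12.

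Both co-primary endpoints use the Week 12 value. A difference between this analysis and the primary one could then come from the window cut and not from the visit timing under test.

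**Working it through.** **Inputs.** Study Day 1 is the first dose (SAP 5.1). The scheduled day is 7 × week + 1 (Appendix F). The visit window is ± 3 days (Protocol Table 2 and 7.2.1). The intervals are those of Tables 12-1 and 12-2.

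**Scheduled days.** 7 × 8 + 1 = 57, 7 × 10 + 1 = 71 and 7 × 12 + 1 = 85, which agree with both tables.

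**Permitted Week 12 days.** 85 − 3 = 82 to 85 + 3 = 88, which is seven days.

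- Table 12-1: all seven satisfy 77 < d ≤ 91, so 0 of 7 are misassigned.
- Table 12-2: Days 82, 83 and 84 satisfy 63 < d ≤ 84 and go to Week 10. Days 85-88 go to Week 12. So 3 of 7 are misassigned.

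**Closest-record rule.** A record on Days 64-81 lies at most max(71 − 64, 81 − 71) = 10 days from Day 71. Days 82, 83 and 84 lie 11, 12 and 13 days away. If any record exists on Days 64-81, the Week 12 sample therefore always loses and is dropped. If none exists, it can become the Week 10 value. Week 12 is then missing unless another sample falls on Days 85-99.

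**Example patterns for a coded subject** (the day used for Week 10 / Week 12):

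| Lipid sample days | Table 12-1 | Table 12-2 |
|---|---|---|
| 66, 71, 84 (Week 8 late) | 71 / 84 | 71 / missing |
| 57, 79, 83 (Week 10 late) | missing / 83 | 79 / missing |
| 63, 84 (Week 8 late, no Week 10) | missing / 84 | 84 / missing |
| 57, 71, 95 (Week 12 late) | 71 / missing | 71 / 95 |

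In the first row the subject gains nothing: the Week 8 interval is the same in both tables, and an on-time Week 12 value is lost. In the second, Table 12-2 recovers Week 10 at the price of Week 12. The fourth is the case where it works as intended.

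**Which regimens are exposed.** For Q2W the 30-day rule applies to the Week 14 contact, so all three days are open. For QM the Week 12 visit must be at least 30 days after the last dose (Protocol Table 2, footnote a), so the earliest visit is the dose day + 30:

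- Last dose on Day 52 or earlier: 52 + 30 = 82, so Days 82-84 are open. This includes a missed Week 8 dose, where the last dose was at Week 4 (Days 26-32).
- Day 53: 83, so two days are open.
- Day 54: 84, so one day is open.
- Day 55 or later: 85 or later, so none.

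An in-window Week 8 dose falls on Days 54-60, so only a Day 54 dose followed by a Day 84 visit is affected.

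**Size per subject.** The Q2W comparison plans 150 + 75 = 225 subjects, so one lost Week 12 value is 1/225 = 0.4%.

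**The case against.** The strongest reply concerns weight. This is one supportive analysis. An affected subject stays in the repeated-measures model through the other visits, and the design has about 98% stated power per regimen, so no route to a changed conclusion is shown. Several conditions must also coincide: code 953 for a visit other than Week 12, a Week 12 sample on Days 82-84, and no further sample on Days 85-99. The documents do not say how often that happens, and 3 of 7 counts calendar days, not subjects. Relabelling as Week 10 is rarer than dropping, since it needs no record at all on Days 64-81. All of this stands. It limits the importance of the point, but it does not make the assignment correct.

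A second reply is that the cut is a trade-off, because no purely day-based boundary can serve both a late Week 10 and an on-time Week 12 sample on Days 82-84. That is true, and it is why the visit label is needed on those three days. It does not justify giving all three to Week 10.

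A third is that the wider interval could be applied to the coded visit only. Week 10 = (63, 84] would then overlap Week 12 = (77, 91] on Days 78-84, so a label would still be needed, and on more days.

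Finally, an out-of-window early Week 12 sample on Days 78-81 would still go to Week 10 after the change proposed here. That is a real limit, but such a sample is treated no worse than under the present Table 12-2.

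**Conclusion.** The concern holds. Followed exactly, Table 12-2 misassigns 3 of the 7 permitted Week 12 days for lipids, against none under Table 12-1, and no SAP rule lets the nominal visit correct this. The exposure is mainly in Q2W subjects coded for a visit other than Week 12.

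The primary analysis, the co-primary tests and the multiplicity steps are unaffected. The effect on the sensitivity estimate cannot be computed, because the number of code-953 subjects and the visits coded are not given; it may be small or nil. The conclusion rests on reading the rule as applying to all of a coded subject's lipid records, which is what both SAP 9.5.1.1 and Table 9-1 say. It should be corrected because the rule works against the purpose of the analysis and is cheap to repair.

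**What to change.** In the lipid row of Table 12-2, set Week 10 = (63, 81] and Week 12 = (81, 99]. For scheduled samples on Days 82-84, let the recorded nominal visit decide, so that a late Week 10 sample stays in Week 10. Keep day-based assignment for samples with no Week 10 or Week 12 label, such as Early Termination samples; on Days 82-84 these then go to Week 12, as in Table 12-1.

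All seven permitted Week 12 days then satisfy 81 < d ≤ 99, so on-time, correctly labelled Week 12 samples stay in Week 12. Of the seven days that Table 12-2 adds to Week 10 (78-84), four (78-81) remain there by day alone, and only three need the label. The late Week 10 pattern above (57, 79, 83) keeps both values: Day 79 for Week 10 and Day 83 for Week 12. The late Week 12 sample on Day 95 is still recovered.

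The cost is one table row and one derivation rule in one sensitivity analysis. It is a small departure from the purely day-based algorithm of Appendix F. No new data are needed, since the data-cleaning example in Protocol 12.3 shows that results carry a visit label.

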### **Handling multiple records assigned to an analytical study week:**

If there is more than one record in a study week interval, the analytical record for that specific study week will be defined as the record closest to the scheduled visit day of that specific study week ( $7 \times$  study week + 1). If two records are equidistant from the scheduled day, then the earlier record will be chosen. If there are multiple records on the same day, the last record will be used.
